Study Population:	This is a pilot study of 40 subjects. We will enroll men and woman 18 – 75 years of age. Patients with alcohol and drug addiction will be

	excluded. Our patient population mostly represents the New York state area, mostly Long island and Queens as we are the main referral hospital to that area.
Phase:	N/A
Description of Sites/Facilities Enrolling Participants:	The Northwell system has a policy that most subarachnoid hemorrhages admitted to our affiliated hospitals get transferred to the Northshore University Hospital Neurosurgical Care Unit as it is the tertiary Neuro-interventional and Neurosurgical Unit of the system. As a result, those patients are automatically transferred to our unit, where screening and enrollment can be initiated.
Description of Study Intervention:	The intervention consists of a transcutaneous non-invasive stimulation of the cervical branch of the vagus nerve (nVNS) using gammaCore, an FDA approved device for the treatment of migraine and cluster headache. This will be compared to the sham device, which is the same device which does not stimulate the nerve. Stimulation frequency will be identical to the frequency used in previous nVNS studies for the treatment of migraine headache. Dosing will be as described in this protocol. The IRB approved healthcare provider will show the subject how to stimulate the cervical branch of the Vagus nerve transcutaneously, and will increase the amplitude/intensity gradually. If pain or discomfort is felt, the amplitude will be decreased to a comfortable level. Rescue pain killers (acetaminophen, opiates) will be given as needed. In the sham group, the sham device will be applied in the same location and at the same frequency as in the treatment group.
Study Duration:	Study period is up to 10 days starting 24 hours post successful treatment of the aneurysm.

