1.2 SCHEDULE OF ACTIVITIES (SOA)

Procedures	Screening and randomization Days -1-5	Enrollment/Baseline Days 2-5 till discharge from NSCU	Step down unit Neurosurgical floor	Final Study discharge
Informed consent	Х			
Demographics	х			
Medical history	Х			
Administer study intervention		Х	x	
Concomitant medication review	х	Х	х	x
Physical exam (including height and weight)	х	Х	x	х
Vital signs (temperature, BP, HR, Oxygen saturation)	х	Hourly and as needed	x	х
Height	Х			
Weight	Х	Х		Х
Performance status	Х	Х	x	Х
Hematology	Х	Х	x	
serum chemistry	Х	Х	X	
Pregnancy test	Х			
EKG (as indicated)	Х	х	As needed	
Daily narcotic use	х	х	x	
Adverse event review and evaluation	х	х	x	x
Radiologic/Imaging assessment (CT, MRI, CTA/CTP, angiogram)	х	х	x	x
Patient satisfaction assessment				x
Complete Case Report Forms (CRFs)	х	х	x	Х

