4 STUDY DESIGN

4.1 OVERALL DESIGN

This is a single site, randomized sham controlled, double blinded, and parallel group study comparing the efficacy and safety of transcutaneous VNS in the management of headache

related to subarachnoid hemorrhage. We will screen patients diagnosed with subarachnoid hemorrhage who are admitted to Northshore University Hospital Neurosurgical Critical Care Unit. These are patients admitted under our care. Eligible patients will be enrolled after signing the informed consent. Enrollment will be performed between days 1 and 5 of aneurysm treatment. Subjects will be randomized into one of the two groups below:

- 1. Group 1: Control (patients will receive treatment using an inactive VNS device)
- 2. Group 2: Treatment (patients will receive treatment using an active VNS device)

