4.4 END OF STUDY DEFINITION

The study intervention will be up to 10 days in length. Vagus stimulation will be performed 4 times daily (approximately at 6:30AM, 11:30AM, 4:30PM and 9:30PM). Data collection will continue till hospital discharge. If the participant becomes hemodynamically unstable, defined as hypotension requiring vasopressors the VNS will be held for safety purposes. However, it will be resumed, once the patient is stabilized, off vasopressors for 48 hours. If the patient is being hemodynamically augmented for symptomatic vasospasm, n-VNS will not be withheld as the beneficial effects of n-VNS on symptomatic vasospasm will be investigated in this study.

Participants must fulfill all of the inclusion criteria in order to be eligible for the study:

- Established signed and dated informed consent form
- Can be enrolled within 5 days of cerebral aneurysm treatment.
- CT of the head revealing blood in the subarachnoid space
- Subject has ruptured cerebral aneurysm or SAH patients who do not have vascular malformation on cerebral angiogram.
- Subject is male or female 18 -75 years of age
- Subject is alert able to verbalize pain at the time of enrollment
- Subject reports pain of 7 and greater on a 10 Point Pain numeric rating scale or presenting with severe headache.
- Female of reproductive age must have a negative pregnancy test (Urine or blood test)

nVNS will only be performed if vital signs are stable (HR>60, SBP> 100 mmHg, MAP> 60 mmhg, and saturation > 90% on room, nasal cannula or face mask). Then the vagus nerve will be stimulated.

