5.5 STRATEGIES FOR RECRUITMENT AND RETENTION

The neurosurgical critical care unit (NSCU) at Northshore University Hospital is the main referral unit for the healthcare system for patients with subarachnoid hemorrhage. All transferred patients

are admitted to the NSCU, as a result, patients can be easily identified by the research team on a daily basis. Every day, the neurointensivist or the research coordinator will evaluate which patients admitted to the NSCU have been diagnosed with subarachnoid hemorrhage. If an aneurysm is found to be the cause of the SAH, surgical or endovascular treatment of the aneurysm is typically performed within 72 hours of diagnosis. Patients will be included in the study once the aneurysm has been treated. The primary investigator, or sub investigators will take consent from the patient. The primary investigator will ensure that the sub investigators and research assistants are trained and knowledgeable of the research protocol. Patients enrolled in the study will be followed up to 10 days starting 24 hours post successful treatment of the aneurysm unless discharged earlier from the hospital.

We admit on average 110 SAH cases a year. If we assume that 50% satisfy our inclusion criteria, and that 70% will sign the inform consent, we should be able to reach our target number in approximately 12 months. Patients identified in the NSCU will be approached by the research team, and the study will be explained to them.

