
Screening involves reviewing the medical records following HIPPA regulation for: Age, gender, ethnicity, presence of aneurysm, day of rupture, etiology of the SAH if not aneurysmal, radiologic (Angiogram, CT head) and medical history before and after the aneurysm is secured, Glasgow coma score before and after aneurysm repair, modified fisher scale (mFS), Hunt-Hess grade (HHS), time of ictus, history of alcohol and drug abuse, presence of hydrocephalus on head CT, presence of an external ventricular drain (EVD), date of EVD placement, new HHS after EVD placement, clipping or coiling. Medical records will be reviewed for the past medical history (pacemaker, defibrillator, history of CHF, arrhythmias, cervical carotid disease, history of a headache disorder like migraine or cluster headache), physical examination, labs will be reviewed which includes but not limited to pregnancy test and urine toxicology. Headache intensity and opiate, steroids and acetaminophen usage are recorded in the electronic medical record. The presence of vasospasm and delayed cerebral ischemia will be noted. Once found eligible satisfying the inclusion and exclusion criteria, and informed consent signed, patients will be randomized to either the treatment group or the control group. The same data will be recorded for both groups. The treatment period will start once admitted in the NSCU and will last for up to 10 days.

During the NSCU stay, patients areevaluated for pain every 4 hours. If vital signs are stable (SBP> 100 mmHg and HR> 60 beats per minutes with no arrhythmia on telemetry, MAP> 60 mmHg and oxygen saturation > 90%) patient will receive either the treatment (nVNS) or the Sham device every 5 hours. Headache intensity will be evaluated every four hours. In addition, vital signs will be noted just after stimulation, and hourly afterwards or as ordered by the physician. The daily mean morphine equivalence dosage will be recorded. Concomitant medications will be recorded.

During the ICU length of stay, the following will be assessed and recorded per standard of care :

- Transcranial dopplers (TCD)
- Neuroimaging (CT head, MRI brain, angiograms, CT perfusion with permeability study)
- EVD weaning and day of start of weaning
- Presence of vasospasm, delayed cerebral ischemia, Central fever, Cerebral salt wasting. These are usually recorded in the medical record.
- Urinary retention documented as frequent straight catheterization for more than 3 days

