8.2 SAFETY AND OTHER ASSESSMENTS

nVNS has been proven to be safe. However, the risks of VNS in SAH population are not known. In order to minimize the risks, if an aneurysm has been identified to be the cause of the SAH, patients will only be enrolled if the aneurysm has been completely treated. This information will be pulled from the medical record. Past medical and surgical history, respiratory and hemodynamic state will be pulled from the medical record. Vital signs and neurologic examinations are usually performed every 1 to 4 hours depending on the acuity of each case, and pain assessment evaluated every 4 hours and as needed. In the NSCU, patients are on continuous ECG analyzes via telemetry. Stimulation will only be given if HR >60 and the SBP>100 mmHg, MAP> 60 mmHg and oxygen saturation is >90% for safety concerns. The presence of intolerable pain at the stimulation site, skin irritation, hoarseness, and change in the taste, shortness of breath, chest pain, nausea, and vomiting will be evaluated.

Safety outcomes:

- Rate of Symptomatic bradycardia defined as a drop in HR to less than 60 beats per minutes with symptoms, not due to nimodipine. The timing of nimodipine relative to the VNS will be recorded. All patients are on telemetry during the stimulation.
- Rate of drop in blood pressure, defined as a drop in blood pressure requiring fluid resuscitation or vasopressor support thought to be due to the device.
- Rate of side effects: presence of intolerable pain at the stimulation site, skin irritation, nasopharyngitis, hoarseness, dysgeusia, shortness of breath, chest pain, nausea and vomiting.

Figure

Days 1-3	Screening			
 Total n=40 Obtain informed consent Screen potential participants by inclusion and exclusion criteria Obtain history, document Randomize 				
Days 2-4 till discha from ICU	rge Baseline assessments/ Study Intervention			
 Obtain daily cumul Evaluate presence Evaluate seizures d Complete vital sign Questionaire for sign 	as before and after each stimulation and daily trend de effects from VNS post every stimulation scranial dopplers (TCD) comatic vasospaspm I fever			
Discharge from the hospital or day 10 post-ictus				

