- Modified ITT (mITT): A modified Intent-to-treat (mITT) population inclusive of all ITT subjects who are treated at least 7 days with at least 3 stimulations of the study device.
- The Per Protocol Set (PPS): Patients who are compliant with the treatment regimen for the duration of the study will be analyzed.
- The safety set will consist of all randomized patients who received at least one stimulation.

The mITT is considered as the primary analysis dataset and will be used for all primary and secondary efficacy analyses. The primary efficacy analyses will be repeated using the PP set. Any discrepancy between the results from the mITT and the PP will be analyzed and discussed.

The secondary variables will be analyzed based on mITT only.

Baseline data and safety analysis will be based on the safety set.

Patient characteristics

In general, data will be summarized by means of summary statistics. Continuous data will be presented with the number of observations, mean value, standard deviation, minimum, median and maximum value. The mean, standard deviation and median will be given with one decimal more than the original values. When applicable, values at each visit, as well as changes from baseline, will be summarized.

Categorical data will be presented as counts and percentages. The data will be presented for each treatment group by visit.

Patient demographics and vital signs will be summarized for all randomized patients. For each of the variables, the treatment group difference will be examined using T-test for continuous variables, and Fisher's exact test for categorical variables.

Efficacy Analysis

The primary analysis of the primary efficacy variable will be based on the mITT population set.

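### The protocol gives no single start and end for the study period, and the SAP's Day 14 contrast and 7-treated-day rule depend on one

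*Protocol*

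**What the plan says.** The protocol describes one period in several places.

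- Synopsis (1.1): "Study period is up to 10 days starting 24 hours post successful treatment of the aneurysm". Section 5.5 repeats the rule for follow-up: "followed up to 10 days starting 24 hours post successful treatment of the aneurysm unless discharged earlier from the hospital".
- Study figure (8.2): the last row reads "Discharge from the hospital or day 10 post-ictus".
- Section 8.1: "The treatment period will start once admitted in the NSCU and will last for up to 10 days".
- Section 4.4: "The study intervention will be up to 10 days in length". Section 4.1 gives the same cap. Neither names a starting event.

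Entry is described just as variously. Section 4.1 has "Enrollment will be performed between days 1 and 5 of aneurysm treatment". The schedule of activities (1.2) heads its second column "Enrollment/Baseline Days 2-5 till discharge from NSCU", while the figure in 8.2 puts screening at Days 1-3 and the intervention at Days 2-4. The schedule and the figure do not say what their days are counted from. The inclusion criteria, printed after 4.4, also admit SAH patients in whom the angiogram shows no vascular malformation.

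The SAP (General approach) takes baseline at Day 1 and the endpoint at Day 14. Its Efficacy Analysis section makes the treatment contrast at Day 14 the primary comparison. Under Analysis populations the mITT is the primary set, made up of "all ITT subjects who are treated at least 7 days with at least 3 stimulations of the study device". The SAP does not link Day 1 to the bleed, aneurysm treatment, enrolment or first stimulation.

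**The concern.** The three anchoring events (bleed, NSCU admission, aneurysm treatment) can lie days apart. Section 5.5 says aneurysm treatment typically comes within 72 hours of diagnosis, and section 4.1 lets enrolment follow as late as day 5 after treatment. The choice of anchor therefore changes how many days of stimulation a patient can receive.

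That matters for the analysis in three ways.

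- **Primary set.** The mITT needs 7 treated days, so the anchor can decide whether a patient is analysed at all. In a pilot of 40, avoidable exclusions are expensive.
- **Visit index.** The MMRM models dose by day. Section 2.1 says the headache worsens over the first week. If Day 1 is not one defined event, the same day number may mix different phases of the illness.
- **Rules that use study duration.** The per-protocol set (compliance over the duration of the study) and the ANCOVA of total dose (adjusted for days in study, 9.4.3) both need a defined period.

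Patients without an aneurysm have no treatment date, so the 24-hour rule gives them no start.

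**Working it through.** The plan has no figure of its own to reproduce here, so the check counts the most days open for stimulation under each reading.

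**Inputs**
- *t* = day of aneurysm treatment after ictus, 0 to 3 (section 5.5, typically within 72 hours of diagnosis).
- *e* = first stimulation, in days after treatment, 1 to 5 (section 4.1).
- Threshold: 7 treated days (SAP, Analysis populations).

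**Assumptions**
- Ictus, diagnosis and NSCU admission all fall on day 0.
- Stimulation starts on the enrolment day.
- The end day counts.
- No day is missed and discharge is not early.

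First stimulation falls on day *s* = *t* + *e*.

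**Maximum days under each reading**
- 10 days of stimulation: 10.
- 24-hour rule, days *t*+1 to *t*+10: (*t* + 10) − *s* + 1 = 11 − *e*.
- Day 10 post-ictus: 10 − *s* + 1 = 11 − *t* − *e*.
- 10 days from NSCU admission, days 0 to 9: 9 − *s* + 1 = 10 − *t* − *e*.

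**Late-enrolment example** (*t* = 3, *e* = 5, *s* = 8)
- Post-ictus: 11 − 3 − 5 = 3 days.
- 24-hour rule: 11 − 5 = 6 days.
- 10 days of stimulation: 10 days (days 8 to 17).

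**Less extreme example** (*t* = 3, *e* = 3)
- Post-ictus: 5 days, out of the mITT.
- 24-hour rule: 8 days, in.
- 10 days of stimulation: 10 days, in.

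**All 20 combinations of *t* and *e***

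| Reading | Range of maximum days | Combinations that can reach 7 |
|---|---|---|
| 10 days of stimulation | 10 | 20 of 20 |
| 24 hours after treatment | 6 to 10 | 16 of 20 |
| Day 10 post-ictus | 3 to 10 | 10 of 20 |
| NSCU admission, read literally | 2 to 9 | 6 of 20 |

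Under the 24-hour rule, 11 − *e* drops below 7 only at *e* = 5. Under the post-ictus end, 7 days need *t* + *e* ≤ 4. Every combination that passes the post-ictus end also passes the 24-hour rule, so those two disagree in 16 − 10 = 6 of 20. Adding the 10-days-of-stimulation reading raises the disagreement to 20 − 10 = 10 of 20. If ictus is called day 1, the post-ictus range becomes 2 to 9 days, with 6 of 20 reaching 7. These are counts over a grid. They are not expected shares of patients, because the documents do not give the distribution of enrolment times.

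**Day 14.** If Day 1 is the first day of intervention, Day 14 falls 14 − 10 = 4 days after the last possible day of stimulation.

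**The case against.** **Fewer rival clocks than a count of sections suggests.** A reader might infer four competing definitions. The documents do not support that. Sections 4.1 and 4.4 give only a cap, which fits the synopsis rule. The sentence in 8.1 follows eligibility, consent and randomisation and may describe where treatment happens; taken literally, it would also clash with the exclusion of unsecured aneurysms in 5.2. This stands. The firm conflict is between the 24-hour rule (1.1 and 5.5) and the figure's last row.

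**The figure may not define the end of treatment.** Its text is poorly preserved and the last row is a bare label. On its own schedule, if its days are post-ictus, starting on Days 2-4 and ending on day 10 leaves 7 to 9 days, so the 7-day rule can be met. This stands as a limit on the example, which joins the figure's end to the entry window in 4.1. But the protocol contains both and does not say which governs.

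**The example is a corner case.** True: it takes the latest enrolment day and the outer treatment delay, and equates ictus with diagnosis. All the periods are also maxima, and the readings converge when treatment and enrolment are early.

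**Consequences.** A reader might infer a bias between arms. Enrolment timing precedes randomisation and the trial is blinded, so nothing here shows one. Selecting the mITT on days treated after randomisation is a separate matter that exists under any clock. Nor should one infer differences between sites in interpretation, since the protocol describes the trial as single site.

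**Data continue past day 10.** Section 4.4 collects data until discharge, so Day 14 values may exist for some patients. They would follow the end of a 10-day intervention and be available only for patients still in hospital.

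**Conclusion.** The point holds as an internal inconsistency. The 24-hour rule and the figure's post-ictus end do not agree. The 8.1 sentence adds a third start if read literally, and patients without an aneurysm have no start under the 24-hour rule. The SAP adds an undefined Day 1 and a primary contrast at Day 14 that does not fit a 10-day intervention.

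The size depends on timing. Late enrolment can move a patient in or out of the primary set: 3, 6 or 10 possible days in the extreme example, and 5, 8 or 10 in the milder one. Under the 24-hour rule alone the problem is narrow, since only a first stimulation on day 5 after treatment rules out 7 days. How many of the 40 would be affected cannot be worked out from the documents.

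The consequence is avoidable loss from the primary set and visit days that may not be comparable across patients. The mITT is primary in the SAP only; Protocol 9.3 lists it without ranking it. The trial is a pilot with no formal hypotheses, but one meant to size a larger study, so exposure length and the day index need to be interpretable. The plan should be corrected on this point.

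**What to change.** 1. **Protocol.** Reconcile the synopsis, the schedule of activities (1.2), 5.5, 8.1 and the 8.2 figure to one stated start and one stated end of the study period, with the start also defined for patients without an aneurysm. Which clinical duration applies is for the investigators; this review does not choose it.
2. **SAP, day index.** Tie Day 1 to one event that exists for every randomised patient. First stimulation is one option, but alone it leaves randomised, never-stimulated patients in the SAP's ITT set without a Day 1, so they need a stated substitute such as the day of randomisation.
3. **SAP, visits and contrast.** Place the modelled visits and the primary contrast within the agreed period. Data collected afterwards, up to discharge, can be kept and summarised descriptively.
4. **SAP, mITT.** Once the period is set, confirm that a patient enrolled on the last permitted day can still reach 7 treated days, or state that such patients are knowingly left out.

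The cost is wording in the protocol and SAP. No new data collection is needed.

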8.3 ADVERSE EVENTS AND SERIOUS ADVERSE EVENTS

8.3.1 DEFINITION OF ADVERSE EVENTS (AE)

Adverse event means any untoward medical occurrence associated with the use of the nVNS and/or Standard of Care Treatments, whether or not considered device-related or drug-related.

8.3.2 DEFINITION OF SERIOUS ADVERSE EVENTS (SAE)

Serious adverse event is defined as in the view of the investigator, the occurrence of any of the following complications:

Death

A life-threatening adverse event such as any hemodynamically unstable arrhythmia Prolongs existing hospitalization

Results in persistent or significant incapacity or disability

Important medical events that may not result in death, be life-threatening, or require hospitalization may be considered serious when, based upon appropriate medical judgment, they may jeopardize the participant and may require medical or surgical intervention to prevent one of the outcomes listed in this definition

8.3.2.1 SEVERITY OF EVENT

For adverse events (AEs) not included in the protocol defined grading system, the following guidelines will be used to describe severity.

- **Mild** Events require minimal or no treatment and do not interfere with the participant's daily activities like skin irritation, transient dysgeusia, transient hoarseness, vomiting, mild pain at the stimulation site during stimulation.
- **Moderate** Events result in a low level of inconvenience or concern with the therapeutic measures. Moderate events may cause some interference with functioning, like mild shortness of breath, chest pain and reversible facial palsy.
- Severe Events interrupt a participant's usual daily activity and may require systemic drug therapy or other treatment. Severe events are usually potentially life-threatening or incapacitating. Of note, the term "severe" does not necessarily equate to "serious". Like hypotension requiring treatement, hemodynamic stable arrhythmia, severe dyspnea requiring medical treatment

